3. Whether there was no new BILAG A organ domain scores and ≤ 1 new BILAG B organ domain score compared to Day 1 will be considered as a dichotomic response with value 1 when it is met and 0 otherwise. This score will be imputed using SAS MI procedure (including 2 other components: SLEDAI-2K change from baseline and PGA score) and the response will be deducted from the logic below:
 - i. Values < 0.5 will be imputed as 0,
 - ii. Values > 0.5 will be imputed as 1.

Components no. 1 to 3 will be imputed assuming a MAR pattern. The SAS MI procedure will be performed as follows:

- Monotone missing data structure will be created as follows: intermediate (non-monotone) missing data will be multiply imputed using the Markov chain Monte Carlo (MCMC) method and assuming MAR and multivariate normality. The SAS procedure PROC MI with the MCMC option will be used with seed number = 2005270018. The number of burn-in iterations will be set to 200, which is the default value. Nevertheless, if diagnosis plots show that the convergence has not yet occurred, this will be adjusted.
- Then, each component will be imputed with treatment group, race, region, SLEDAI-2K total score (<10 ; ≥ 10) and data at previous visit from all SRI components as covariates.

- Imputation will be repeated 1000 times. The SRI response will then be calculated for each of the multiply imputed data sets from the imputed components. For this analysis, the estimated OR, together with associated two-sided 95% CI of the estimated OR and nominal p-value from the logistic regression model, comparing each evobrutinib treatment group to placebo will be presented. Results will be combined using MIANALYZE SAS procedure with the Rubin's rules as described in Appendix 18.9.

The SAS code to implement the MI and MIANALYZE procedures is in Appendix 18.9.

The same analysis method as the primary analysis of the two-primary endpoints will be performed using the mITT Analysis Set for SRI-4 and in the HDA subject subgroup for SRI-6.

In addition, the number and percentage of SRI-4/SRI-6 responders and non-responders at Week 52 in each treatment group will be presented the same way as for the primary analysis (see Section 14.1.2.10) using Rubin's rules to gather binomial proportion by each treatment (see Appendix 18.9).

Sensitivity Analysis #3: Tipping Point Analysis

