18.9.1 SRI Response

Logistic regression: PROC LOGISTIC with SAS

The logistic regression can be implemented using the following SAS code:

```
proc logistic data=<dataset> descending;
  class TreatmentGroup(ref='Placebo') Region Race SLEDAI_2K_screening;
  model AVALC(event="Y") = TreatmentGroup Region Race
                        SLEDAI_2K_screening / orpvalue clodds=wald;
  ods output CLoddsWald=CLoddsWald;
run;
```

For primary analysis of the 2-primary endpoints and key secondary endpoint *SRI-4 response at Week 52 among serologically active subgroup*, output the 1-sided p-value ($\alpha=0.025$) as below:

- When the OR favors the active treatment (i.e. $OR > 1$), one-sided p-value = two-sided p-value / 2
- When the OR does not favor the active treatment (i.e. $OR \leq 1$), one-sided p-value = 1 – (two-sided p-value / 2)

The interaction can be implemented using the “*” symbol. For example, the following statement takes into consideration the interaction between treatment and region:

```
proc logistic data=<dataset> descending;
  class TreatmentGroup(ref='Placebo') Region Race SLEDAI_2K_screening;
  model AVALC(event="Y") = TreatmentGroup Region Race SLEDAI_2K_screening
                        TreatmentGroup * Region / orpvalue clodds=wald;
  ods output ParameterEstimates=ParameterEstimates CLoddsWald=CLoddsWald;
run;
```

Linear trend in log odds of SRI response for two-primary and key secondary endpoints: PROC LOGISTIC with SAS

In addition to the standard logistic model, the linear trend test can be implemented using the ESTIMATE and CONTRAST statements:

```
proc logistic data=<dataset>;
  class TreatmentGroup Region Race SLEDAI_2K_screening / param=glm;
  model AVALC(event="Y") = TreatmentGroup Region Race
                        SLEDAI_2K_screening;
  ESTIMATE "SRI response rate trend linear in treatment" TreatmentGroup 3 1 -1 -
3;
  CONTRAST "SRI response rate trend linear in treatment" TreatmentGroup 3 1 -1 -3
/ e;
  ods output
  Estimates=Estimates ContrastTest=ContrastTest;
run;
```

Logistic regression subgroup analysis: PROC GLIMMIX with SAS

In addition to the standard logistic model, the subgroup analysis can be implemented using the following code:

```
proc glimmix data=<dataset>;
  class TreatmentGroup (ref='Placebo') SLEDAI_2K_screening;
  model AVALC(event="Y") = TreatmentGroup SLEDAI_2K_screening TreatmentGroup*
  SLEDAI_2K_screening / alpha=0.05 dist=binary;

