PROC MIANALYZE DATA=lgsodds_t;
  MODELEFFECTS log_or_lr_value;
  STDERR log_or_lr_se;
  ODS OUTPUT PARAMETERESTIMATES=mian_lgsodds_t;
QUIT;
*** Back-transform combined values;
DATA mian_lgsodds_bt;
  SET mian_lgsodds_t;
  estimate_back = EXP(ESTIMATE); *Pooled odds ratio;
  qn=quantile('NORMAL',.975);
  LCL_back=Estimate_back*EXP(-qn*STDERR); *Pooled lower limit;
  UCL_back=Estimate_back*EXP(+qn*STDERR); *Pooled upper limit;
RUN;

/*****
STEP 4b : Pooling p-value
*****/
PROC MIANLYZE PARMs (CLASSVAR=CLASSVAL)=ParameterEstimatesMI
  CLASS TreatmentGroup;
  MODELEFFECTS TreatmentGroup;
  ODS OUTPUT PARAMETERESTIMATES=mian_logres
QUIT;
```

Then Step 4a and 4b are to be repeated for the analysis of SRI-6.

Pooling binomial proportion in each treatment arm after MI

```
*** Estimate proportions of responders in each treatment arm;
PROC FREQ DATA=datain_mi;
  TABLES resp / cl binomial(level=2);
```

```
Exact binomial;
BY _Imputation_ TreatmentGroup;
ODS OUTPUT BINOMIALPROP=prop;
RUN;
*** From ODS output dataset BINOMIALPROP, create a dataset
containing estimated proportion of responders in each
treatment arm and their standard errors;
DATA prop_trt;
MERGE
prop(WHERE=(Label1="Proportion")
KEEP=_Imputation_ TreatmentGroup nValue1 Label1
RENAME=(nValue1=prop))
prop(WHERE=(Label1="95% Lower Conf Limit")
RENAME=(nValue1=LOWERCL)
prop(WHERE=(Label1="95% Upper Conf Limit")
RENAME=(nValue1=UPPERCL)
qn = Quantile('NORMAL',.975)
prop_se = (UPPERCL - LOWERCL) / (2 * qn)
BY _Imputation_ TreatmentGroup;
RUN;
*** Combine proportion estimates;
PROC SORT DATA=prop_trt; BY TreatmentGroup _Imputation_; RUN;
PROC MIANALYZE DATA=prop_trt;
MODELEFFECTS prop;
STDERR prop_se;
BY TreatmentGroup;
ODS OUTPUT PARAMETERESTIMATES=mian_prop_trt;
RUN;
```

Tipping point sensitivity analysis

*1- Start by computing the number of missing response in each treatment at the willing visit in macrovariables: nmisspbo nmissd1 nmissd2 nmissd3.

*2- Then complete the tipping point analysis:

```
***TIPPING POINT ANALYSIS FOR BINARY DATA;
data resptip
  set resp;
  if TreatmentGroup='Pbo' then trtn=1;
  else if TreatmentGroup='Dose 1' then trtn=2;
  else if TreatmentGroup='Dose 2' then trtn=3;
  else if TreatmentGroup='Dose 3' then trtn=4;
  randnum=ranuni(200527);
  misspbo=&nmisspbo;
  missd1=&nmissd1;
  missd2=&nmissd2;
  missd3=&nmissd3;
run;
***Sort by random number allow cumulative imputation of failure /
success to subjects in random order;
PROC SORT data=resptip; BY randnum; QUIT;

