    SLEDAI_2K_screening / RL TIES=DISCRETE;
  ods output ParameterEstimates=_es; run;

run;

/*****
STEP 5 : Combined estimates
*****/
/* Combine model coefficients. */
proc sort data=_es;
  by Parameter ClassVal0 _Imputation_;
  run;
proc mianalyze data=_es;
  by Parameter ClassVal0;
  modeleffects Estimate;
  stderr stderr;
  ods output ParameterEstimates = _es_mianal;
run;

/*Exponentiate in order to obtain hazard ratio estimates and confidence intervals */
data resprefix_hr;
  set _es_mianal;
  Log_HR_Comb=Estimate;
```

```
HR_comb=exp(Estimate);  
HR_LCL_comb=exp(LCLMean);  
HR_UCL_comb=exp(UCLMean);  
keep Parameter ClassVal0 Log_HR_comb HR_comb HR_LCL_comb HR_UCL_comb Probt;  
rename Probt=HR_pval_comb;  
run;
```

Logistic regression for the flare-free status

The same procedure as in Appendix 18.9.1 must be applied.

NB model for BILAG A Severe flare / BILAG A or 2B Moderate to Severe flare/ SFI Severe flare

The NB model will be performed using the GENMOD procedure from SAS:

```
proc genmod data=<Dataset>;  
  class TreatmentGroup Region Race SLEDAI_2K_screening;  
  model AVAL = TreatmentGroup Region Race SLEDAI_2K_screening/ alpha=0.05  
  offset=LOGTIME  
  DIST=NB MAXITER=<MaxIter>;  
  ESTIMATE "log flare RR evobrutinib 25mg QD vs placebo" TreatmentGroup -1 1 0 0  
  / EXP;  
  ESTIMATE "log flare RR evobrutinib 75mg QD vs placebo" TreatmentGroup -1 0 1 0  
  / EXP;  
  ESTIMATE "log flare RR evobrutinib 50mg BID vs placebo" TreatmentGroup -1 0 0 1  
  / EXP;  
  ods output estimates=estimates1;  
run;
```

where <maxIter> is the number of iteration (must be sufficiently high to run the model). The offset is equal to the logarithm of years on treatment.

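### The sample code for the multiple-imputation sensitivity analysis does not produce the dose-versus-placebo odds ratios and p-values that SAP Section 14.1.2.2 requires

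*SAP*

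**What the plan says.** SAP Section 14.1.2.2, Sensitivity Analysis #2, fixes the comparison and how it is pooled. The odds ratio, its two-sided 95% CI and a nominal p-value, "comparing each evobrutinib treatment group to placebo will be presented. Results will be combined using MIANALYZE SAS procedure with the Rubin's rules", as set out in Appendix 18.9. On the number of imputations it says: "Imputation will be repeated 1000 times. The SRI response will then be calculated for each of the multiply imputed data sets". On the model: "The same analysis method as the primary analysis of the two-primary endpoints will be performed using the mITT Analysis Set for SRI-4", with the HDA subgroup for SRI-6.

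Appendix 18.9.1 gives the code:

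- **Logistic model.** The placebo-referenced blocks use "class TreatmentGroup(ref='Placebo') Region Race SLEDAI_2K_screening" with no `PARAM=` option. Only the trend-test block sets a parameterisation (`param=glm`).
- **Step 4a.** A filter is meant to keep every treatment odds ratio. The log odds ratios then go into "PROC MIANALYZE DATA=lgsodds_t", which has a MODELEFFECTS and a STDERR statement but no BY statement.
- **Step 4b.** The p-value comes from a separate call on the model coefficients, "PROC MIANLYZE PARMs (CLASSVAR=CLASSVAL)=ParameterEstimatesMI", with TreatmentGroup as the class effect.

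Elsewhere the same appendix does pool by group. The responder proportions are pooled by TreatmentGroup (18.9.1), and the Cox estimates for time to flare are pooled "by Parameter ClassVal0" (18.9.2).

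**The concern.** The text asks for three comparisons with placebo per endpoint. The code appears to give one odds ratio across all doses (Step 4a) and three p-values that may not refer to placebo (Step 4b).

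The first fault comes from the missing BY statement. MIANALYZE treats every row it receives as a draw of the same quantity.

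The second comes from a software default. In PROC LOGISTIC, `ref=` without `PARAM=REF` leaves effect coding in place and only selects the omitted level. Each treatment coefficient is then that dose's log odds minus the unweighted mean log odds of all four arms. The odds-ratio table from the same model is still dose versus placebo, so the two outputs of one fit answer different questions.

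At stake is the credibility of one planned check on the rule that counts a missing Week 52 response as non-response. The check could make a real effect look fragile, make a dose equal to placebo look different from it, or print a p-value that disagrees with the confidence interval beside it.

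**Working it through.** The plan states no figure on this point, so there is nothing to reproduce. The check compares what the code estimates with what the text requires.

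**Inputs**

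- 103 evaluable subjects per arm, 40% SRI-4 response on placebo and a 20-point improvement, hence 60% on active: SAP Section 8.2.1.
- 1000 imputations, three doses against placebo: SAP Section 14.1.2.2.
- Assumed: complete data (no between-imputation variance), no covariates, normal approximation, two-sided p. Any rates other than 40% and 60% are illustrations.

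**Building blocks.** Logit(0.60) = 0.405 and logit(0.40) = −0.405. The variance of an arm's log odds is 1/(n·p·q) = 1/(103 × 0.24) = 0.0405 at either rate.

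**Step 4b, 40% on placebo and 60% on every dose**

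- Required comparison: log OR = 0.405 − (−0.405) = 0.811. SE = √(2 × 0.0405) = 0.284. z = 2.85, p = 0.0044, OR = 2.25.
- Effect-coded coefficient: the mean of the four log odds is (−0.405 + 3 × 0.405)/4 = 0.203, so the coefficient is 0.405 − 0.203 = 0.203 (unrounded 0.2027). With weights (3/4, −1/4, −1/4, −1/4), SE = √(0.75 × 0.0405) = 0.174. z = 1.16, p ≈ 0.245.

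Logistic models fitted to 100 subjects per arm at the same rates show the same pattern: p = 0.005 under reference coding and 0.25 under effect coding.

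**Step 4b, error in the other direction (illustrative rates 40/40/60/60%)**

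- The lowest dose equals placebo: OR 1.00, p = 1.00.
- The mean log odds of the four arms is 0, so its effect-coded coefficient is −0.405. SE = 0.174, z = −2.33, p = 0.020.

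**Step 4a (illustrative rates 40/40/50/60%)**

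- Rows pooled: 3 × 1000 = 3000, all treated as draws of one parameter.
- True log ORs: 0, 0.405 and 0.811 (ORs 1.00, 1.50 and 2.25). Their mean is 0.405, so the single pooled OR is 1.50.
- Mean within-row variance: (0.0809 + 0.0793 + 0.0809)/3 = 0.0804.
- Variance between rows, which here is purely the spread between doses: about 0.1096.
- Total: 0.0804 + 0.1096 × (1 + 1/3000) ≈ 0.190. SE = 0.436, against about 0.28 for any one comparison. The 95% CI is 0.64 to 3.53.
- Pooled by comparison, the same data give three ORs, with p = 1.00, 0.150 and 0.0044.

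The Step 4a fault does not depend on how the model is coded. The Step 4b fault does.

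**The case against.** The governing text is right and the fault lies in an appendix headed as sample code. That limits the point but does not remove it. The appendix opens by saying that it details how the methods will be implemented, and Section 14.1.2.2 refers to it for the pooling.

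The logistic call that creates the data set read by Step 4b is not printed. The displayed primary block outputs only the odds-ratio table, and coefficients are output only in the interaction example. A reader might therefore infer that the Step 4b p-values certainly compare each dose with the four-arm mean. The document supports this only conditionally. It follows if the call uses the displayed CLASS statement, which the instruction to use the primary method implies. The effect-coding default is a property of SAS and is not stated in the SAP.

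The code also cannot run as printed. The procedure name in Step 4b is misspelled, semicolons are missing, and the Step 4a filter looks for `TRT`, which does not occur in the name TreatmentGroup. Someone must edit it, and a single odds ratio where the table needs three would probably be noticed. That stands for Step 4a. It is weaker for Step 4b, which would give plausible rows labelled by dose. Repairing the syntax cures neither fault.

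A reader might also infer that the primary result or the type I error is at risk. It is not. The primary analysis reads the odds-ratio table, which is already dose versus placebo. Sensitivity 2 reports nominal p-values outside the hierarchy of Section 14.1.2.4. Nor does the SAP rank it as the main missing-data check: the tipping-point analysis (Sensitivity 3) tests the same rule with separate code.

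**Conclusion.** The point holds as a conflict between the analysis specified in Section 14.1.2.2 and the pooling code in Appendix 18.9.1. It should be fixed, but it does not threaten the primary analysis or any success decision.

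Step 4a, once made to run, gives one odds ratio in place of three and counts differences between doses as imputation variance. This is read directly from the code. Step 4b gives p-values against the four-arm mean log odds, provided that the unprinted logistic call uses the displayed CLASS statement.

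At the design rates with 103 per arm, p moves from 0.0044 to about 0.245. That figure rests on complete data, no covariates and 60% response on all three doses. The actual size depends on the observed rates, the mITT numbers and, for SRI-6, the smaller HDA subgroup.

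**What to change.** In Step 4a, make the row filter match the treatment effect name, sort by treatment comparison and imputation, and run MIANALYZE BY treatment comparison. Take the p-value from that same pooled log odds ratio, so that OR, CI and p-value come from one estimate, and delete Step 4b. The coding question then no longer arises, because the odds-ratio table is already dose versus placebo. If Step 4b is kept instead, add `/ param=ref` to the CLASS statement of the logistic model fitted to each imputed data set, and print that call in the appendix.

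The code change is a few lines. The real cost is checking. This SAP version was written after the primary analysis results had been reviewed and the study terminated, so any Sensitivity 2 output already produced from this code must be checked against the program actually used and rerun where it carries either fault.

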For this analysis, a subject will be considered as an SRI-4 or SRI-6 Non-Responder if the subject takes EAC-determined protocol-prohibited medications during the treatment period (i.e. EAC-treatment failure).

Tipping point analysis will be performed as in Yan 2009, Section 2.3.2.

All possible combinations of success/failure may be posited in the 4 treatments groups. Results are obtained by a random single imputation of possible scenarios (responder or non-responder) to each arm. All possible combinations of imputations of response among subjects with missing response in the placebo group and evobrutinib 25 mg QD, 75 mg QD and 50 mg BID groups. For each combination, the imputed data were combined with the data from subjects with non-missing data and primary analysis.

Assumptions of missing data due to a missing response at Week 52 will be varied to see if there are any tipping points:

Let

$n_1 =$ number of responders out of missing data due to various reasons for placebo

$n_2 =$ number of responders out of missing data due to various reasons for evobrutinib 25 mg QD

$n_3 =$ number of responders out of missing data due to various reasons for evobrutinib 75 mg QD

$n_4 =$ number of responders out of missing data due to various reasons for evobrutinib 50 mg BID

The same analysis method as the primary analysis of the two-primary endpoints will be performed using the mITT Analysis Set for each possible combination of n_1 , n_2 , n_3 and n_4 .

The values of n_1 , n_2 , n_3 and n_4 where the study result will be tipped from statistically significant (not statistically significant) to not statistically significant (statistically significant) will be assessed for plausibility based on the corresponding response rate from each treatment. See Section 14.1.2.4 for the multiplicity adjustment procedure.

Sensitivity Analysis #4: Unadjusted Analysis

The analysis of the two-primary endpoints will be performed on the mITT Analysis Set.

In this analysis, the logistic regression model will be used with only treatment as a factor.

For this analysis, the estimated OR, together with associated two-sided 95% CI of the estimated OR and nominal p-value from the logistic regression model, comparing each evobrutinib treatment group to placebo will be presented.

In addition, the number and percentage of SRI-4/SRI-6 responders and non-responders at Week 52 in each treatment group will be presented the same way as for the primary analysis (see Section 14.1.2.1).

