DATA resptip2
  SET resptip;
  WHERE trtn in (1 2 3 4);
  ARRAY randcount(4);
  ARRAY t(4);
  *Each missing data will be identified by its number starting from 1, by each
treatment;
  RETAIN randcount 0;
```

```
newresp=resp;
IF resp=. THEN randcount(trtn)+1;
*Output misspbo*missd1 + misspbo*missd2 + misspbo*missd3 scenarios, ie all possible
combination of pbo with the dose;
DO t1=1 to misspbo
  DO t2=1 TO missd1;
  DO t3=1 TO missd2;
  DO t4=1 TO missd3;
  IF resp=. THEN DO;
    IF randcount(trtn)<=t(trtn) THEN newresp=1;
    ELSE newresp=0;
    OUTPUT;
  END;
  ELSE OUTPUT;
END;
END;
END;
END;
```

*3- Then apply primary analysis to the new dataset according to each tipping point scenarios (ie by t1 t2 t3 t4).

From that we could plot p-value of each dose versus pbo.

Looking at t1 vs t2 for the p-value of dose 1.

Looking at t1 vs t3 for the p-value of dose 2.

Looking at t1 vs t4 for the p-value of dose 4.

*Label variable in result dataset that will be displayed in plot;

```
data p;
set pvalue;
label pvalue="P-value"
  t1='N of responders among missing - Placebo'
  t2='N of responders among missing - Dose 1;
  t3='N of responders among missing - Dose 2;
  t4='N of responders among missing - Dose 3;
run;
*Select scenarios and treatment to plot;
%macro selscenartrt (scenarios=, trtnum=,out=)
  data &out.;
  set p;
  where bygroup in (&scenarios) and trtn in (&trtnum.)
%mend selscenartrt;
%selscenartrt (scenarios=%str("t1" "t2"), trtnum=%str(1 2),out=pt1t2)
%selscenartrt (scenarios=%str("t1" "t3"), trtnum=%str(1 3),out=pt1t3)
%selscenartrt (scenarios=%str("t1" "t4"), trtnum=%str(1 4),out=pt1t4)
```

*Plot the wanted comparison;

```
proc sort data=pt1t2;
  by t1 t2;
quit;
proc sgplot data=p;
  title1 "Adjusted p-value 1-side : Placebo vs Dose 1";
  heatmapparm x=t2 y=t1 colorresponse=pvalue / colormodel=TwoColorRamp discretex
discretex transparency=0.2 OUTLINE outlineattrs=(thickness=0.5pt color=gray);
  text x=j y=i text=nvalue2 / textattrs=(size=5pt) strip;
  gradlegend;
```

```
footnote1 justify=left "Placebo: N (ITTm) = xxx1, Observed Resp = xxresp1, Observed  
Non-Resp = xxnresp1 and Missing = &nmisspbo.";  
footnote2 justify=left "Dose 1: N (ITTm) = xxx2, Observed Resp = xxresp2,  
Observed Non-Resp = xxnresp2, Missing = &nmissd1.";  
run;
```

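### The tipping-point code in Appendix 18.9.1 starts all four loops at one imputed responder, so it skips every scenario with none in an arm, including the primary scenario and both extremes

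*SAP*

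**What the plan says.** The governing text is Sensitivity Analysis #3 in Section 14.1.2.2: "All possible combinations of success/failure may be posited in the 4 treatments groups". It defines n1 to n4 as the numbers of responders among the missing in the four arms. It asks for the primary method at each combination of them and looks for flips in both directions, from significant to non-significant and the reverse. Table 17 likewise promises the study conclusion at each combination. Section 14.1.2.1 sets the primary rule: a missing Week 52 response counts as non-response, which is the scenario with zero imputed responders in all four arms.

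The code in Appendix 18.9.1 numbers the missing subjects from 1 within each arm ("IF resp=. THEN randcount(trtn)+1") and makes the first t of them responders ("IF randcount(trtn)<=t(trtn) THEN newresp=1"). The plot label for t1, "N of responders among missing - Placebo", confirms what t means. The loops are "DO t1=1 to misspbo", "DO t2=1 TO missd1", "DO t3=1 TO missd2" and "DO t4=1 TO missd3", nested, with every OUTPUT statement inside the nest. A comment above them gives the number of scenarios as the sum of three placebo-by-dose products.

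**The concern.** Since t counts imputed responders and never falls below 1, every scenario the code creates turns at least one missing subject in every arm into a responder. The text asks for all combinations, and zero is one of them.

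Two things are at stake. First, the grid has no cell equal to the primary analysis, so nothing ties the display back to the reported p-value. Second, the extreme edges are where a tipping point may sit. Dropping the edge with no responders among a dose arm's missing can leave a significant result looking as if it never tips. Dropping the edge with no responders among the placebo missing can do the same for a non-significant one.

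**Working it through.** **Inputs.** Loop bounds, numbering and imputation rule: Appendix 18.9.1. Primary rule: Section 14.1.2.1. One-sided level 0.025: Section 14. Arm size of about 108 and 5% drop-out: Section 8.2.1, used only for illustration. The numbers of missing responses are assumptions, because the SAP gives none.

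**1. The plan's own scenario count.** With 5 missing per arm, the comment's sum is 5×5 + 5×5 + 5×5 = 75. The nested loops as written give the product 5×5×5×5 = 625. All combinations, with 0 to 5 in each arm, number 6⁴ = 1,296. At 10 per arm the three figures are 300, 10,000 and 14,641. The code matches neither its own comment nor the text of Section 14.1.2.2.

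**2. Which points are missing.** In the order (placebo, dose 1, dose 2, dose 3), three points never occur whatever the counts:
- (0, 0, 0, 0), the primary rule;
- (misspbo, 0, 0, 0), the worst case for the drug;
- (0, missd1, missd2, missd3), the best case for the drug.

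**3. Cells lost for one dose against placebo, m missing in each arm.** Lost: (m+1)² − m² = 2m+1. Of these, m have no dose responders and at least one placebo responder (adverse to the drug), m have no placebo responders and at least one dose responder (favourable), and one is the primary scenario.

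| m | full grid | lost | adverse | favourable | primary |
|---|---|---|---|---|---|
| 5 | 36 | 11 | 5 (14%) | 5 | 1 |
| 10 | 121 | 21 | 10 (8%) | 10 | 1 |
| 25 | 676 | 51 | 25 (3.7%) | 25 | 1 |

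**4. Whether a flip can be hidden.** Assume 108 per arm, 5 missing in each, and an unadjusted one-sided Wald test of the log odds ratio, z = ln(OR)/SE, with SE² the sum of the reciprocals of the four cell counts. Compare p with 0.025.

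*Significant primary result*, 43 placebo and 62 dose responders:
- primary, 43 v 62: ln(OR) = 0.712, SE = 0.277, z = 2.57, p = 0.005;
- true worst case, 48 v 62: z = 1.90, p = 0.029, tipped;
- worst case the code runs, 48 v 63: z = 2.04, p = 0.021, not tipped.

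*Non-significant primary result*, 43 placebo and 53 dose responders:
- primary, 43 v 53: z = 1.37, p = 0.086;
- true best case, 43 v 58: z = 2.04, p = 0.021, tipped;
- best case the code runs, 44 v 58: z = 1.90, p = 0.0285, not tipped.

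The counts were chosen to fall in the gap. They show that a hidden flip is possible, not that it is likely.

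**5. An arm with no missing response.** A loop from 1 to 0 makes no pass, and every OUTPUT lies inside the nest. With missing counts (5, 5, 0, 5) the code writes 5×5×0×5 = 0 scenarios for any dose. Started at 0, it writes 6×6×1×6 = 216.

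**The case against.** The governing text is right, and the slip is only in an appendix headed as sample code. As printed, that code lacks semicolons and closing quotes, so a programmer would have to rework it and could do so from Section 14.1.2.2. This limits the seriousness but does not remove the point: Section 18.9 says that the appendix sets out how the methods will be implemented, and the loop bounds are logic, not typography. With missing data in every arm, starting at 1 raises no warning and gives a plausible heatmap without its zero row and column.

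Several stronger readings are tempting, and the SAP does not support them.
- *That the lost cells are all adverse to the drug.* Only m of the 2m+1 are. The grid still reaches the scenario with all placebo missing as responders and a single dose responder, so a hidden flip needs a margin of about one subject. Section 14.1.2.2 also judges tipping values for plausibility, and the extreme corners are the least plausible.
- *That an empty output is likely, or would mislead.* It depends on the data. Assume about 54 high-disease-activity subjects per arm (half of 108) and independent missingness. The chance of no missing response in at least one of four arms is then 1 − (1 − 0.95⁵⁴)⁴ = 23% at 5% missing and 1 − (1 − 0.90⁵⁴)⁴ = 1.3% at 10%. Section 7 mentions drop-out potentially higher than expected. An empty data set would also be noticed.
- *That the four-way nesting is the defect and should give way to separate two-way grids.* Section 14.1.2.2 asks for four-arm combinations and refers to the multiplicity procedure in Section 14.1.2.4. Under that procedure a lower dose is tested only after the higher one succeeds, so the study conclusion depends on all arms jointly. The nesting follows the plan; only the comment's count is wrong.

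**Conclusion.** The code is wrong as written and contradicts Section 14.1.2.2 and Table 17. It leaves out zero imputed responders in every arm, and with it the primary scenario and both extremes. A tipping point can be missed in either direction, but only where significance changes between one and zero imputed responders in an arm. Per dose, the adverse cells lost are 14% of the grid at 5 missing per arm and 3.7% at 25. The missing counts and the responder numbers in the illustration are assumptions; the omission of the zero scenarios is not. The primary test is unaffected. The consequence is confined to one named sensitivity analysis, and the correction is worth making because it is specific and cheap.

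**What to change.** In Appendix 18.9.1:
- Start all four loops at 0 (`DO t=0 TO n`). A loop from 0 to 0 runs once, so an arm with no missing response no longer empties the output.
- Keep the four-way nesting.
- Correct the comment to (misspbo+1)(missd1+1)(missd2+1)(missd3+1) scenarios.
- Add a check that cell (0,0,0,0) reproduces the primary p-values.

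Two-way displays per dose may be added for presentation but should not replace the four-arm grid. Sections 6.3 and 6.4 say that the primary analysis results have already been reviewed. If the existing tipping-point output came from this code, rerun it.

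The cost is a few characters of code and more model fits: 1,296 instead of 625 scenarios at 5 missing per arm, or 14,641 instead of 10,000 at 10.
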